4.2.6.2 Laboratory variables

Observed values and changes from baseline of laboratory data for haematology, clinical chemistry and fasting lipid profile will be summarised by visit. The summary statistics presented will be minimum, 1st quartile, median, 3rd quartile, maximum, mean, and SD.

Shift plots (scatter plots) for each of the parameters presenting baseline values versus minimum post-baseline values and maximum post-baseline values, respectively, will be provided. A diagonal line indicating no change and horizontal and vertical reference lines indicating the limits of the reference ranges will also be displayed on the shift plots.

If any laboratory variables show any unusual features (high or low values or a general shift in the data points) at specific visits, then shift plots of these data may also be produced. This will be discussed and agreed upon during the BDR meeting.

For each laboratory parameter with available criteria, the number and percentage of subjects with TELVC values will be summarised by visit. Additionally, the number and percentage of subjects with at least one TELVC value will be presented.

The number and percentage of subjects with laboratory values below, within or above the corresponding normal range will be presented by visit. Urinalysis will be summarised as shift tables from baseline to the last on-treatment value for each parameter. Furthermore, the number and percentage of subjects with treatment-emergent changes will be summarised by parameter. In addition, observed values and change from baseline and pre-specified categories will be summarised by visit for any continuous variables.

In order to identify potential Hy's Law cases, the number and percentage of subjects in categories based on multiples of ULN for maximum on-treatment ALT and AST by maximum total bilirubin will be presented in a table. The table will include the following categories: < and $\geq 2xULN$ for total bilirubin and < $3xULN$, $\geq 3 - < 5xULN$, $\geq 5 - < 10xULN$ and $\geq 10xULN$ for ALT/AST.

Individual subject data will be presented for all subjects who meet the criteria for potential Hy's law. The relevant laboratory parameters (ALT, AST, total bilirubin and ALP) will be tabulated showing all visits for these subjects. Subjects with elevated ALT or AST (ALT or AST $\geq 3 \times \text{ULN}$) and elevated total bilirubin ($\geq 2 \times \text{ULN}$) at any time during the study (not necessarily at the same time) will be included.

4.2.6.3 ECGs

The number and percentage of subjects with normal, abnormal, not clinically significant and abnormal, clinically significant ECG results will be presented as a shift table from baseline to last observation on treatment.

Individual ECG parameters will not be summarised or analysed as the data is not collected.

4.2.6.4 SLEDAI-2K-based flare assessment instrument

The flare rate per of subject years for extra-renal flares will be presented overall, and by timing ("on-treatment" and "off-treatment"), for mild/moderate flares, severe flares and any flares, respectively. An "on-treatment" flare is defined as a flare with a date of onset after the date of first dose of IP and on or prior to the date of last dose of IP + 28 days. An "off-treatment" flare is defined as a flare with a date of onset after the date of last dose of IP + 28 days. Where a flare has been marked as both mild/moderate and severe, it will be considered to be severe for the purposes of this summary.

4.2.6.5 Vital signs

Observed values and changes from baseline of pulse, systolic blood pressure, diastolic blood pressure, respiration rate and body temperature, respectively, will be summarised by pre, during and post infusion, time, visit and treatment group. As multiple values are recorded during infusion and post-infusion, the average value during infusion and the average value post-infusion will also be calculated for each subject at each visit (along with the change from baseline for these average values) and these will be included in the summary tables along with the individual values.

For each parameter with available criteria, the number and percentage of subjects with TELVC values will be summarised by visit. Additionally, the number and percentage of subjects with at least one TELVC value will be presented.

For each parameter, the number and percentage of subjects with values below, within or above the corresponding normal range will be presented by visit. In addition, this information will be presented as shift tables from baseline to each post-baseline visit.

Observed values and changes from baseline of body weight and BMI will be summarised.

4.2.6.6 Cushingoid features

The number and percentage of subjects will be summarised for each feature by visit and treatment group. For subjects with baseline OCS ≥ 10 mg/day prednisone or equivalent, the summary will be repeated by OCS status at Week 52 (target OCS dose of ≤ 7.5 mg/day

reached versus target OCS dose of ≤ 7.5 mg/day not reached) and at Week 104 (target OCS dose of ≤ 5.0 mg/day reached versus target OCS dose of ≤ 5.0 mg/day not reached).

4.2.6.7 C-SSRS

The number and percentage of subjects with suicidal ideation (overall and by maximum category), suicidal behaviour (overall and by maximum category), and no suicidal ideation or behaviour will be presented by treatment group for assessments during screening, during treatment, and during follow-up, respectively.

Furthermore, descriptive statistics on the total number of attempts, total number of interrupted attempts and total number of aborted attempts will be summarised by treatment group for attempts during screening, during treatment and during follow-up, respectively.

Subjects with a suicidal ideation or behaviour at any time up until Week 52 will be presented in a listing.

4.2.6.8 Personal Health Questionnaire Depression Scale-8

Observed values and changes from baseline in PHQ-8 total score will be presented with descriptive statistics by visit and treatment group.

4.2.7 Analysis methods for pharmacokinetics, pharmacodynamics, and immunogenicity

If not stated otherwise, all analyses of pharmacodynamics and immunogenicity will be performed for the full analysis set by treatment group. If not stated otherwise, all analyses of pharmacokinetics will be performed for the PK analysis set by treatment group.

4.2.7.1 Analysis methods for immunogenicity variables

The proportion of subjects with ADA results as described in Section 3.7.1 will be presented together with descriptive statistics of the available titres. Descriptive statistics will include n (number of reportable titres), minimum, quartiles (1st quartile, median and 3rd quartile) and maximum.

ADA response and the corresponding titre will be summarised at baseline and at all scheduled post-baseline visits in the study period by treatment group for the full analysis set. In addition, the proportion of ADA positive subjects will be presented cumulatively.

A summary of key subject information will be provided for ADA positive subjects.

The analyses of impact of ADA on PK and PD endpoints are described in Sections 4.2.7.2 and 4.2.7.3.

Pre-specified AE categories and hypersensitivity events during the on-treatment period will be summarised by ADA status (positive, negative).

Additional summaries of immunogenicity data may be generated based on the results of the above analyses.

4.2.7.2 Analysis methods for pharmacokinetic variables

Anifrolumab serum concentrations will be summarised using descriptive statistics by visit reporting n (number of non-missing values), m (number of non-zero values), geometric mean, geometric CV%, arithmetic mean, SD, arithmetic CV%, median, minimum and maximum. If applicable, this summary will be repeated including individual concentrations excluded from descriptive statistics.

Serum concentration-time profiles of anifrolumab by treatment group will be generated as plots of mean values (including SD) by time point in a semi-log scale and a linear scale. This will be presented for all values and additionally for values measured before administration (C_{trough}).

The potential influence of demographic covariates such as body weight, race, sex and age will be explored. Furthermore, potential correlation between anifrolumab concentrations and 21-gene type IFN PD signature will be explored. These analyses will be performed by MedImmune's Clinical Pharmacology and Drug Metabolism and Pharmacokinetics (DMPK) group.

Impact of ADA on PK will be explored by spaghetti plots of individual concentration data over time using different styles by ADA result (positive at any time/negative). This will be presented for all values and additionally for values measured before administration (C_{trough}). Summaries of anifrolumab serum concentrations by visit and ADA status (positive, negative) will be presented.

Mycophenolic acid serum concentrations will be summarised using descriptive statistics as specified above at each visit by treatment group. Serum concentration-time profiles of MPA by treatment group will also be generated. Analyses of mycophenolic acid serum concentrations will be performed on the full analysis set.

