3.7 Pharmacokinetics, pharmacodynamics, and immunogenicity

3.7.1 Immunogenicity variables

Anti-drug antibodies (ADA) assessments will be conducted utilising a tiered approach (screen, confirm, titre).

The proportion of subjects with ADA responses during the treatment and follow-up periods will be summarised. Anti-drug antibody response categories summarised will include (but are not limited to):

- ADA prevalence: a positive ADA result at any visit including study baseline and all post-baseline measurements
- ADA negative: does not meet criteria for ADA positive
- Subjects who are ADA positive at baseline only
- Subjects who are ADA positive post-baseline only
- Subjects who are ADA positive at both baseline and post-baseline
- Subjects who are ADA positive by visit
- Subjects who are ADA positive at a post-baseline measurement for the first time (for subjects who are ADA negative at baseline) by visit
- ADA persistently (4 months) positive: positive at ≥ 2 post-baseline assessments, with ≥ 16 weeks between first and last positive or positive at last post-baseline assessment (for subjects who are ADA negative at baseline)
- ADA prolonged (6 months) persistently positive: positive at ≥ 2 post-baseline assessments, with ≥ 24 weeks between first and last positive or positive at last post-baseline assessment (for subjects who are ADA negative at baseline)
- ADA prolonged (12 months) persistently positive: positive at ≥ 2 post-baseline assessments, with ≥ 48 weeks between first and last positive or positive at last post-baseline assessment (for subjects who are ADA negative at baseline)
- ADA transiently (<4 months) positive: at least 1 post-baseline ADA positive assessment and not fulfilling the conditions of ADA persistently positive (for subjects who are ADA negative at baseline)

- ADA positive with titre \leq median of maximum titre. To calculate the median of maximum titre, take the maximum value for each subject, then calculate the median of these values across all subjects (for subjects who are ADA negative at baseline and ≥ 1 post-baseline ADA result available).
- ADA positive with titre $>$ median of maximum titre (for subjects who are ADA negative at baseline and ≥ 1 post-baseline ADA result available).
- Neutralising antibody (nAb) incidence: post-baseline nAb positive result only (not positive at baseline)

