4.2.7.3 Analysis methods for pharmacodynamic and lupus serology variables

IFN21 gene PD signature as percent of baseline IFN21 PD signature will be summarised by time point for subjects who are IFN test-high at randomisation. The median absolute deviation (MAD) will also be included in this summary. Furthermore, the median percent of baseline IFN21 PD signature (including MAD) over time will be presented as a line plot for the same population.

The impact of ADA on IFN21 gene PD signature will be explored. For IFN test-high subjects, IFN21 gene PD signatures as percent of baseline IFN21 PD signature will be summarised descriptively by ADA status (ADA negative/positive at any time) and ADA positive subgroups (ADA persistently/prolonged persistently positive, ADA titre > median, ADA nAb positive) by timepoint and treatment group.

For subjects who are positive for anti-dsDNA at baseline and abnormal complement level at baseline, respectively, observed values and changes from baseline of anti-dsDNA, C3 and C4 complement levels will be summarised by visit, providing the frequency of positive data allows.

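### The concentration plots and the main IFN21 summary label subjects by ADA positive at any time, so values from before the first positive sample count as ADA-positive; the status used in the concentration table is undefined

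*SAP*

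**What the plan says.** Protocol 8.5.6 says that the impact of ADA on PK and PD endpoints will be assessed, and leaves the method to the SAP.

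- **Concentration plots (SAP 4.2.7.2).** Individual concentrations over time are plotted "using different styles by ADA result (positive at any time/negative").
- **Concentration table (SAP 4.2.7.2).** "Summaries of anifrolumab serum concentrations by visit and ADA status (positive, negative) will be presented". No timing rule for the status is given.
- **IFN21 (SAP 4.2.7.3).** In IFN test-high subjects, percent of baseline is summarised by "ADA status (ADA negative/positive at any time) and ADA positive subgroups (ADA persistently/prolonged persistently positive, ADA titre > median, ADA nAb positive"), laid out "by timepoint and treatment group".
- **Definitions (SAP 3.7.1).** The nearest definition of being positive at any time is "ADA prevalence: a positive ADA result at any visit including study baseline and all post-baseline measurements". The other group is its complement: "ADA negative: does not meet criteria for ADA positive", with no minimum number of samples. The same section also lists "Subjects who are ADA positive by visit" and, for subjects negative at baseline, the visit of the first post-baseline positive. Neither variable is linked to the PK or IFN21 analyses.

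**The concern.** Whether ADA lowers exposure or weakens target suppression is a question about what happens once ADA is present. A label fixed by the whole ADA record answers a different one: do subjects who are positive at some point differ at a given visit? A subject first positive at Week 60, twelve weeks after a last dose at Week 48, would have every concentration and IFN21 value from Weeks 12 to 52 shown as ADA-positive. If the nearest definition applies, a subject positive only at baseline would be treated in the same way.

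The label also depends on how long a subject is followed, and that depends on outcome. SAP 1.2.5 requires the renal part of the partial response definition for entry to year 2, and year 2 brings more ADA samples. Protocol 1.2.4 names possible loss of drug through proteinuria as one reason for the higher starting dose. Ever-positive status could therefore be mixed up with renal response and, through that, with exposure.

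At stake is how the ADA-impact section of the study report is read, not a confirmatory conclusion.

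**Working it through.** The documents give no ADA incidence, no time to seroconversion and no expected difference in concentration or IFN21, so there is no stated figure to reproduce. The sample counts below come from the protocol. The rest is illustration under assumed values.

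**Step 1. Scheduled ADA samples (Protocol Tables 2 to 5).**

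- Both paths: Weeks 0, 12, 24, 36 and 52.
- No extension: plus Weeks 56 and 60. Post-baseline total 4 + 2 = 6.
- Extension: plus Weeks 68, 84, 104, 108 and 112. Post-baseline total 4 + 5 = 9.

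Weeks 56 and 60 on the first path, and 108 and 112 on the second, are off-drug follow-up visits.

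**Step 2. Chance of being labelled positive.** Assume a constant chance h per post-baseline sample. Then P(ever positive) = 1 − (1 − h)^k, with k = 6 or 9.

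| Assumed h | k = 6 | k = 9 | Ratio |
|---|---|---|---|
| 0.5% | 3.0% | 4.4% | 1.49 |
| 2% | 11.4% | 16.6% | 1.46 |
| 5% | 26.5% | 37.0% | 1.40 |

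If the chance instead accrues per week (0.0005 to 0.005) over 60 against 112 weeks, the ratio runs from 1.84 down to 1.65.

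**Step 3. Dilution in a group summary.** Suppose that concentration falls by a factor r from the first positive sample onward, and that subjects not yet converted look like negatives. If a share s of ever-positive subjects has converted by a visit, the apparent geometric mean ratio is r^s. With conversions spread evenly over Weeks 12, 24, 36 and 52:

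| Visit | s | True r = 0.50 | True r = 0.70 |
|---|---|---|---|
| Week 12 | 0.25 | 0.84 | 0.91 |
| Week 24 | 0.50 | 0.71 | 0.84 |
| Week 36 | 0.75 | 0.59 | 0.77 |
| Week 52 | 1.00 | 0.50 | 0.70 |

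This table assumes that nobody converts after Week 52. If first positives are instead spread evenly over all scheduled post-baseline samples, a true 0.50 reads 0.89, 0.79, 0.71 and 0.63 at Weeks 12, 24, 36 and 52 on the 6-sample path (s = 1/6, 2/6, 3/6, 4/6). On the 9-sample path it reads 0.93, 0.86, 0.79 and 0.73 (s = 1/9, 2/9, 3/9, 4/9). Under the same assumptions, status defined up to and including each visit returns r at every visit.

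The ratios describe a table of geometric means. They do not describe the individual plots, which yield no group ratio. Nor do they carry over numerically to IFN21, which is summarised with medians; there only the mechanism is shared.

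**Step 4. Do the IFN21 subgroups cure the timing problem?** Persistence is judged from the span between positives or from a positive last sample, and the titre group from each subject's maximum titre. The antibody-neutralising group has no timing rule. All are subject-level labels, so values from before conversion stay inside them. On one reading of the persistence wording, a single positive at the final off-drug visit would qualify.

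**Step 5. Is time-matched status available?** Each visit with an IFN21 sample also has an ADA sample. For PK the match has one gap: Protocol Table 2 marks pre-dose and post-dose PK at Week 48, but no ADA sample there.

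**The case against.** The case for leaving the plan alone has several sound parts.

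- **The concentration table is not stated to use the ever-positive label.** A reader might carry the label over from the plots to the table. The SAP does not say so, and the supportable point there is that the status is undefined.
- **The plots show each subject's course.** A fall within a subject stays visible whatever line style is used. A reader might infer that an ADA effect would be hidden; with tables by visit and individual plots, dilution at early visits is as far as the documents go.
- **IFN21 is not judged by ever-positive status alone.** The persistent, titre and neutralising subgroups reduce dilution by transient positives. They do not remove the timing problem.
- **The follow-up difference has no known direction.** A reader might infer that the analysis leans towards finding no ADA effect, because renal responders get more chances to test positive and may keep more drug. That needs ADA incidence and timing and the size of the proteinuria effect, and the documents give none of these; the protocol calls the drug loss only potential. After Week 52 the scheduled on-drug samples come from extension subjects, who share one ADA schedule, so the 6-against-9 contrast bears mainly on first-year visits.
- **Nothing confirmatory depends on this.** The analyses are described as explored, and SAP 4.2.7.1 allows further immunogenicity summaries.

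These points limit the size and priority of the concern. They do not answer the use of future ADA results in the plot label and the main IFN21 grouping, or the missing definition for the table.

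**Conclusion.** The point holds in a limited form. For the concentration plots and the main IFN21 summary, the plan places values from before the first positive sample in the ADA-positive group. For the concentration table it leaves the status open. In a group summary this can pull an ADA effect towards no difference, most at early visits and less as more subjects convert. Under the assumptions in Step 3, a true halving could read anywhere from 0.84 to 0.93 at Week 12 and from 0.50 to 0.73 at Week 52, depending on when conversions occur.

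The 9-against-6 sample count, conditional on renal response, is a fact of the schedule. What it does to the comparison, in size or net direction, cannot be derived from the documents.

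Priority is low, because the analyses are exploratory and descriptive and no primary or secondary test is touched. It is still worth correcting, because this is the plan's stated assessment of ADA impact and the variables needed are already derived.

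**What to change.** In SAP 4.2.7.2 and 4.2.7.3:

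1. For the by-visit concentration table and the IFN21 summary by timepoint, define ADA status at each visit from samples up to and including that visit, positive from the first post-baseline positive onward. Use the by-visit and first-positive variables in SAP 3.7.1.
2. Show baseline-positive subjects as a separate group.
3. Mark the first positive sample on each subject's line in the spaghetti plots.
4. Keep the ever-positive summaries alongside if wanted, labelled as such.

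The cost is SAP wording and programming, with no new data. There are two downsides. Early visits will have fewer ADA-positive observations. Week 48 PK, which supplies the maximum concentration after the last first-year dose, has no ADA sample and would carry the Week 36 status; a footnote should say so.

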4.2.7.3 Analysis methods for pharmacodynamic and lupus serology variables

IFN21 gene PD signature as percent of baseline IFN21 PD signature will be summarised by time point for subjects who are IFN test-high at randomisation. The median absolute deviation (MAD) will also be included in this summary. Furthermore, the median percent of baseline IFN21 PD signature (including MAD) over time will be presented as a line plot for the same population.

The impact of ADA on IFN21 gene PD signature will be explored. For IFN test-high subjects, IFN21 gene PD signatures as percent of baseline IFN21 PD signature will be summarised descriptively by ADA status (ADA negative/positive at any time) and ADA positive subgroups (ADA persistently/prolonged persistently positive, ADA titre > median, ADA nAb positive) by timepoint and treatment group.

For subjects who are positive for anti-dsDNA at baseline and abnormal complement level at baseline, respectively, observed values and changes from baseline of anti-dsDNA, C3 and C4 complement levels will be summarised by visit, providing the frequency of positive data allows.

4.3 Subgroup analysis

To explore the uniformity of the detected overall treatment effect, subgroup analyses will be performed for the following factors:

- Type I IFN 4-gene test at screening (IFN test-high, IFN test-low)
- 24-hour UPCr at screening ≤ 3 mg/mg, >3 mg/mg
- Age (≥ 18 to 64, ≥ 65 years)
- Placebo response region (low placebo response rate versus high placebo response rate)
Countries with a low placebo response rate versus high placebo response rate are defined as [Low: Australia, Belgium, France, Germany, Italy, South Africa, Spain, United Kingdom, United States], [High: Argentina, Hungary, Republic of Korea, Mexico, Peru, Poland, Russian Federation, Serbia, Taiwan]
- Race (white; black or African American; Asian, native Hawaiian or other Pacific Islander; American Indian or Alaska native; other)
- Screening biopsy classification (class III, class IV, mixed [class III or IV + class V])
- Number of methylprednisolone pulses (1, >1). Pulses are counted during the whole study.
- ADA result (Positive at any time, Negative)
- OCS at baseline (<20 mg/day, ≥ 20 mg/day)
- eGFR at baseline (<60 mL/min/1.73m², ≥ 60 mL/min/1.73m²)

Table 3, Table 4 and Table 5 give an overview of subgroup analyses to be performed at Week 24, 52 and Week 104, respectively. Where necessary (e.g. for subgroup analysis based on stratification factors), the model factors will be reduced. If not stated otherwise, the subgroup analysis will not be performed for a sub-population if any treatment group consists of less than 10 subjects within that sub-population. Where a sub-population contains less than 10 subjects in any treatment group, only ns and treatment estimates will be presented (no treatment comparisons will be presented).

Forest plots will be used to summarise the estimates of the treatment effect for the applicable subgroups.

Table 3 Overview of subgroup analyses at Week 24

Analysis	IFN test	24-hour UPCR	OCS at baseline
24-hour UPCR	X	X	X
CRR	X	X	X

Table 4 Overview of subgroup analyses at Week 52

Analysis	IFN test	24-hour UPCR	Age	Placebo response	Race	Number of methylprednisolone pulses	Screening biopsy	ADA result	OCS at baseline	eGFR at baseline
24-hour UPCR	X	X	X	X	X	X	X	X	X	X
CRR	X	X	X	X	X	X	X		X	X
aCRR	X	X							X	
PRR	X	X				X	X			
Graded CRR	X	X				X	X			
OCS tapering	X	X		X		X	X			

Table 5 Overview of subgroup analyses at Week 104

Analysis	IFN test	24-hour UPCR	OCS at baseline	eGFR at baseline
24-hour UPCR	X	X	X	X
CRR	X	X	X	X

Analysis	IFN test	24-hour UPCR	OCS at baseline	eGFR at baseline
PRR	X	X		
Graded CRR	X	X		
OCS tapering	X	X		

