3.1 Inclusion criteria

For inclusion in the study subjects should fulfil the following criteria:

1. In the opinion of the investigator, must be able to understand the informed consent form (ICF), and all protocol-related subject assessments
2. Men and women, age 18 through 70 years at the time of screening
3. Written informed consent and any locally required authorisation (eg, Health Insurance Portability and Accountability Act [HIPAA] in the US, Data Privacy Directive in the European Union [EU]) obtained from the subject prior to performing any protocol-related procedures, including screening evaluations
4. Fulfils at least 4 of the 11 ACR classification criteria for SLE (see [Appendix E](#)), one of which must be:
 - (a) Positive antinuclear antibody (ANA) test (1:40 or higher) at screening by immunofluorescence assay at central laboratory; **or**
 - (b) Elevated anti-dsDNA antibodies at screening (reported as equivocal or positive results), as per the central laboratory; **or**
 - (c) Anti-Smith antibody at screening elevated to above normal (ie, positive or equivocal results) as per the central laboratory

Clinical criteria may be present by history if documented in the medical record. Historical laboratory values can be counted for SLE criteria but at least one of the values specified above must be met at screening for eligibility.

5. Weigh ≥ 40.0 kg at screening
6. Diagnosis of proliferative LN based on a renal biopsy obtained within 12 weeks prior to signing the ICF or during the screening period:
 - Class III (\pm Class V) or Class IV (\pm Class V) LN according to the World Health Organisation (WHO) or 2003 ISN/RPS classification (based on local evaluation of renal biopsy)
7. Urine protein to creatinine ratio >1 mg/mg (113.17 mg/mmol), obtained on a 24-hour urine collection at both:
 - The start of screening and

- Within 14 days prior to the expected date of randomisation. Without the results of the second (stratification) sample, subjects cannot be randomised. Turn-around time for results from central laboratory is up to 7 days.
8. Estimated glomerular filtration rate (as calculated by the MDRD formula, with screening laboratory results for serum creatinine value) ≥ 35 mL/min/1.73 m²
 9. Negative serum β -human chorionic gonadotropin (β -hCG) test at screening (females of childbearing potential only)

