1.3 Number of subjects

A total of approximately 150 subjects will be randomised 1:1:1 to receive one of the two IV anifrolumab dosing regimens (Basic Regimen or Intensified Regimen) or placebo.

The sample size is based on the following assumptions:

- Reductions from baseline to Week 52 in 24-hour UPCR of 65% and 46% for the anifrolumab and placebo arms, respectively (i.e., ratios of 24-hours UPCR from Week 52 to baseline of 0.35 and 0.54, respectively), based on data presented in (Furie R, 2014).
- The change from baseline in the log-transformed 24-hour UPCR values follow a normal distribution with a standard deviation (SD) of 0.8, based on data from the anifrolumab Phase 2b study (CD1013)

Based on these assumptions, a sample size of 50 subjects per arm would result in an observed relative difference in the change from baseline to Week 52 in 24-hour UPCR of 0.65 (here expressed as the ratio, comparing anifrolumab to placebo), and a corresponding 95% confidence interval (CI) of (0.50, 0.85) comparing the pooled anifrolumab group (Basic and Intensified) with placebo group. Under the assumption that the interim analysis is performed

with 120 subjects, a 0.001 2-sided alpha will be spent, and the final analysis will be based on a 2-sided alpha of 0.0499 (East Version 6.4). If the study is not stopped for futility, this sample size provides approximately 87% power for the primary analysis with a 2-sided alpha of 0.0499 to reject the hypothesis of no effect (relative difference =1) for comparing the pooled anifrolumab treatment group with placebo. The minimal detectable relative difference in the change from baseline to Week 52 in 24-hour UPCR between the pooled anifrolumab treatment group versus placebo is approximately 0.76, corresponding to a reduction from baseline to Week 52 in 24-hour UPCR of 59% in the pooled anifrolumab group (ratio of 24-hour UPCR from Week 52 to baseline of 0.41).

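### The subgroup plan sets out to explore uniformity of effect but reports no treatment-by-subgroup estimate or interval, so a reader is left to compare separate subgroup intervals by eye

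*SAP*

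**What the plan says.** SAP Section 4.3 lists ten factors and opens with its aim: "To explore the uniformity of the detected overall treatment effect, subgroup analyses will be performed for the following factors". The display is stated as "Forest plots will be used to summarise the estimates of the treatment effect for the applicable subgroups". Model factors are reduced where needed, for example when the subgroup is itself a stratification factor, which points to separate models fitted inside each subgroup. A size rule applies: "the subgroup analysis will not be performed for a sub-population if any treatment group consists of less than 10 subjects" within that sub-population. In that case only counts and estimates are shown, with no comparison.

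Section 4.3 is not redacted and contains no treatment-by-subgroup term, contrast, interval or test. The only interaction in the primary model (SAP Section 4.2.1) is treatment by visit. Protocol Section 8.5.10 lists the factors and leaves the full details to the SAP, so nothing elsewhere in the plan supplies the contrast. SAP Section 4.1.3 provides 95% CIs for treatment comparisons. It also allows nominal p-values outside the error-control strategy, with the caveat that they carry no claim of significance.

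**The concern.** Whether an effect is uniform depends on the difference between subgroup effects. The plan gives the reader two intervals side by side and leaves that difference unstated. The usual shortcut is to note that one interval excludes 1 and the other does not. That shortcut answers a different question and is heavily driven by subgroup size.

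This matters most for the factors people will want to act on. Protocol Section 5.7.4 says the IFN test will be evaluated for development as a companion diagnostic, and Section 4.3 splits countries by expected placebo response. In both cases the question is about a difference in effect, and the plan prints no estimate of it.

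**Working it through.** **Inputs (SAP Section 1.3).** "A total of approximately 150 subjects will be randomised 1:1:1 to receive one of the two IV" regimens or placebo, so 100 pooled anifrolumab versus 50 placebo. "Reductions from baseline to Week 52 in 24-hour UPCR of 65% and 46% for the anifrolumab and placebo arms, respectively", so the ratio is 0.35/0.54 = 0.648 and its log is −0.434. The log change is assumed to follow a "normal distribution with a standard deviation (SD) of 0.8". No dropout allowance is stated there, so none is applied. Subgroup sizes are not given in the documents, so the splits below are assumptions.

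**The plan's own figure.** SE = 0.8 × √(1/50 + 1/100) = 0.1386. Normal-approximation power at two-sided 0.0499 is 0.879 (0.874 with the rounded ratio 0.65; 0.870 to 0.875 with a t distribution). This agrees with the stated "approximately 87% power for the primary analysis with a 2-sided alpha of 0.0499". The stated CI of 0.50 to 0.85 and minimal detectable ratio of 0.76 also reproduce.

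**Split decisions under a uniform effect.** For a placebo subgroup of size n with 2n on anifrolumab, SE = 0.8 × √(1/n + 1/(2n)). Let p1 and p2 be the chances that each subgroup's 95% CI excludes 1. The chance that exactly one does is p1(1 − p2) + p2(1 − p1). For the even split this is 2 × 0.60 × 0.40 = 0.48.

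| Split | Placebo n | SEs | p1, p2 | Exactly one excludes 1 | Opposite directions |
|---|---|---|---|---|---|
| 50:50 | 25, 25 | 0.196, 0.196 | 0.60, 0.60 | 48% | 3% |
| 70:30 | 35, 15 | 0.166, 0.253 | 0.74, 0.40 | 55% | 5% |
| 80:20 | 40, 10 | 0.155, 0.310 | 0.80, 0.29 | 63% | 8% |

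For the even split, both intervals exclude 1 in 36% of trials and neither does in 16%. Sensitivity for the even split: true ratios of 0.60, 0.70 and 0.76 give 38%, 49% and 41%, and SDs from 0.7 to 1.0 give 41% to 50%.

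**The direct contrast.** The log ratio of treatment ratios has SE √(SE1² + SE2²). That is 0.277 for 50:50 and 0.346 for 80:20. Its 95% CI wrongly excludes 1 in 5% of uniform-effect trials (0.050 in simulation). The interval reaches a factor of exp(1.96 × 0.277) = 1.72 either way for the even split, and exp(1.96 × 0.346) = 1.97 for 80:20. For 80% power in the even split the true ratio of effects would have to be exp(2.80 × 0.277), about 2.2.

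**Week 104 UPCR row.** The size rule counts the sub-population, whereas only subjects meeting the Week 52 continuation criteria stay on IP, and SAP Section 4.2.1 excludes data after IP discontinuation. The following is illustrative: 10 subjects per arm, the UPCR criterion only, plan ratios and SD, baselines assumed. For baselines at or below 3 mg/mg, the expected number continuing is 10 × Φ(ln(1/(baseline × ratio))/0.8).

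| Assumed baseline (mg/mg) | Anifrolumab | Placebo |
|---|---|---|
| 1.5 | 7.9 | 6.0 |
| 2.5 | 5.7 | 3.5 |
| 3.0 | 4.8 | 2.7 |
| 4 to 6 (criterion for >3: more than 50% improvement) | 6.7 | 4.6 |

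A comparison could therefore be printed with well under 10 values per arm at that visit.

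**The case against.** **No significance rule is set.** The SAP nowhere tells the reader to compare which intervals exclude 1, and Section 4.1.3 warns against reading significance into nominal p-values. In simulation of the even split the two intervals overlap in 99.4% of trials. Among the split-decision trials they overlap in 98.8%, and both estimates favour anifrolumab in 97%. This stands: the 48% to 63% describes a common misreading, not a planned inference.

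**The contrast can be derived.** Two complementary estimates with CIs determine the ratio of ratios and roughly its SE. That is so, but the reader should not have to compute the one quantity the section exists to examine.

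**The remedy has its own noise.** At 5% each, ten factors would give at least one false exclusion in 1 − 0.95¹⁰ = 40% of trials if independent (34% for the eight baseline factors). This is a reason to label the contrasts and lead with the estimate, not a reason to omit them.

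**The 63% is at the display limit.** With 20% prevalence, the smaller subgroup reaches the 30 subjects needed for 10 per arm in only about 53% of trials even if perfectly balanced. Otherwise no comparison is shown.

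**Two stronger inferences are tempting and not supported.**
- *Age.* Eligibility is "Men and women, age 18 through 70 years at the time of screening" and the cut is at 65, so a reader might infer that the age row cannot meet the minimum. If ages were spread evenly, about 5.7 of 50 per arm would be 65 or over. The chance of reaching 10 is then about 3.6% for placebo and the pooled group (0.051 × 0.71), and about 0.0001 if all three arms must reach it. That is very unlikely but not impossible, and the section already withholds the comparison in that case. Nothing in the documents makes a different age cut necessary.
- *Week 104.* A reader might infer that all Week 104 subgroup results rest on too few data. The responder endpoints use non-responder imputation through Week 104 (SAP Section 4.1.4.3), so subjects who stop IP stay in the denominator. Only the UPCR row loses them, and its model also draws on earlier visits.

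**Conclusion.** The point holds as a reporting gap in an exploratory section. The plan states an aim of uniformity and omits the between-subgroup estimate. It does not invalidate any planned analysis and does not touch the primary or secondary tests.

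The size, about 48% for an even split and 55% to 63% for uneven ones against 5% for the direct contrast, rests on four conditions: 24-hour UPCR at Week 52; the planned effect and SD with no dropout; a two-level factor with the assumed split; and a reader who compares which interval excludes 1. It should not be read as the chance that subgroup effects will point in different directions. The figures do not extend to CRR, because the documents give no assumed response rates, or directly to race and biopsy class, which have more than two categories.

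**What to change.** 1. For each baseline factor in SAP Tables 3 to 5, fit treatment-by-subgroup-by-visit, with its lower-order terms, in the MMRM on all subjects. Print on the forest plot the ratio of treatment ratios at the visit with its 95% CI.
2. For CRR, print the difference between the subgroup risk differences with its 95% CI.
3. Label these contrasts exploratory and unadjusted for multiplicity. Leave out the number of methylprednisolone pulses over the whole study and ADA at any time, which are determined after randomisation.
4. For the Week 104 UPCR row only, apply the 10-subject rule to subjects with an analysed value at that visit.

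The cost is SAP wording and one extra forest-plot column, with no change to conduct, sample size or alpha. The intervals will be wide (a factor of about 1.7 for an even split and 2.0 for 20:80), and some may exclude 1 by chance across the factors. The estimate with its interval should therefore be reported in place of a test result.
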